5. STUDY OUTCOMES

5.1 Primary Outcome

The primary outcome of the study will be death or poor neurologic outcome at six months. Neurologic outcome will be assessed using the Disability Ratings Scale (DRS), an 8-item ordinal scale that evaluates functional dependence.¹¹ The DRS has both reliability and validity in the assessment of neurologic function following traumatic and acquired brain injury.^{1,8} Neurologic outcome will be assessed by a specialist in rehabilitation medicine. Patients will be judged to have had a poor neurologic outcome if the score on the DRS scale is >5.

5.2 Secondary Outcomes

- 1) Death during the initial hospitalization, at 30 days and at 6 months
- 2) Stroke during the initial hospitalization, and at 6 months
- 3) TIMI minor/major bleeding during first hospitalization (+7 days)
- 4) Length of stay in the unit
- 5) Length of stay in the hospital
- 6) Cardiogenic shock during the initial hospitalization
- 7) Repeat circulatory arrest requiring cardiopulmonary resuscitation (CPR)
- 8) Arrhythmia requiring anti-arrhythmic medication (aside from beta blocker)
- 9) Presence of seizures
- 10) Renal failure requiring renal replacement therapy
- 11) Ventilator associated pneumonia
- 12) LV function assessed by echo done on day 3 and at 90 days
- 13) CK release within first 48 hrs.
- 14) Frequency of Stent thrombosis
- 15) Discharged home.

All clinical events will be adjudicated by a committee utilizing the abovementioned definitions in a blinded manner. As noted, rehabilitation physicians performing the neurologic assessments will be blinded to group allocation.

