4.2.4 Randomization

Randomization will be performed in a 1:1 fashion by sealed opaque envelopes and treatment assigned by random number generation done in blocks. Patients will be randomized immediately following insertion of the endovascular cooling catheter. Because patients with ventricular tachycardia (VT) or ventricular fibrillation (VF) have better survival than other rhythms¹⁰ patients will be stratified based on their initial rhythm. Patients with an initial rhythm of either VT or VF will be randomized from a different series of envelopes than patients with an initial rhythm of asystole or pulseless electrical activity (PEA). The two different series of randomization

envelopes will be identifiable and differentiable by coding (ie. VT/VF randomization codes will begin by the number 1, while randomization codes for asystole/PEA will begin by the number 2). This will ensure balancing in the groups in this important prognostic factor.

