4.3 Interventions

Eligible patients will be randomized to mild TH (goal cooling temperature of 34°C) or moderate TH (goal cooling temperature of 31°C). The rate of cooling to the signed temperature after randomization will be on the basis of as fast as technically feasible by the device. Cooling will be performed via an endovascular cooling device (ZOLL Medical Corporation, Chelmsford, MA) inserted via the femoral vein into the inferior vena cava either in the cardiac catheterization laboratory or in the coronary care unit. Our current practice is to target 33°C with the identical protocol. Paramedics and transferring facilities will be encouraged to initiate hypothermia with ice packs as soon as possible (prior to arrival at the University of Ottawa Heart Institute). This is done by placing ice packs to the neck, groin and axilla.

Upon presentation to the University of Ottawa Heart Institute, patients may be taken to the cardiac catheterization laboratory at the discretion of the treating team for coronary angiography and/or insertion of a mechanical support device (intra-aortic balloon pump).

All patients will be sedated, intubated and ventilated. The University of Ottawa Heart Institute standard cooling protocol will be used to implement sedation, analgesia and neuromuscular blockade. Paralytic agents will be used during the cooling process to inhibit shivering. All of these medications and monitoring are currently the standard of care. The temperature will be recorded via the ZOLL catheter. Patients will have nasopharyngeal and bladder temperature probes inserted to correlate with temperatures monitored intravascularly.

Patients who present to the Ottawa Heart Institute with body temperatures $<34^{\circ}\text{C}$ can still be randomized to one of the groups. The temperature will be adjusted with the endovascular cooling device according to the randomly assigned temperature. Note that the device is capable at cooling or warming to the set target temperature.

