6.4 Cardiogenic Shock

Systolic blood pressure < 80 mm Hg not responding to fluid expansion, and requiring the use of intravenous inotropic support or the use of intra-aortic balloon counterpulsation.

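### Cardiogenic shock is counted over the whole hospitalization rather than from randomization, so shock present before allocation is scored as an outcome and pulls the comparison toward no difference

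*Combined protocol and SAP*

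**What the plan says.** **Outcome windows (section 5.2).** Shock is listed as "Cardiogenic shock during the initial hospitalization". Bleeding is listed as "TIMI minor/major bleeding during first hospitalization (+7 days", again with the hospital stay as the window. Drug-treated arrhythmia, seizures ("Presence of seizures") and renal replacement have neither a start nor an end time.

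**Definitions (section 6).** Of these five outcomes, section 6 defines only bleeding and shock. Section 6.4 requires a systolic pressure under 80 mm Hg that fluids do not correct, together with support: "requiring the use of intravenous inotropic support or the use of intra-aortic balloon counterpulsation". It says nothing about when the episode must begin. Sections 7 to 7.3 give no rule for dating events or for handling conditions already present at baseline.

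**Time of allocation.** Section 4.2.4: "Patients will be randomized immediately following insertion of the endovascular cooling catheter". Section 4.3 places that insertion in the catheterization laboratory or the coronary care unit. It also says that on presentation the treating team may take the patient for "coronary angiography and/or insertion of a mechanical support device (intra-aortic balloon pump".

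**Eligibility.** Section 4.2.3 does not exclude shock, seizures, anti-arrhythmic treatment or dialysis. The order set in Appendix 9 lists refractory shock as an exclusion, but section 4.2.2 gives that order set only a guiding role in selection.

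**The concern.** A comparison of randomized arms can attribute to treatment only what happens after allocation. The window for shock opens at admission, and allocation comes later in the same admission. The patients are comatose survivors of cardiac arrest, so low pressure needing support between those two times is foreseeable. Balloon counterpulsation is one of the two support criteria in section 6.4, and section 4.3 allows a balloon pump on presentation.

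At stake is how informative the shock comparison is. Section 4.3 names hypotension refractory to vasopressors as a reason to abandon cooling, so shock is among the closest comparative measures of a harm that the protocol itself anticipates. A background of events that treatment cannot influence makes a real difference between 31°C and 34°C, in either direction, harder to see.

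**Working it through.** **1. The plan's own figure.** Inputs from sections 3.6.1 and 8.1: 50% versus 35%, alpha 0.05, power 80%, 1:1 allocation. With m the mean of the two risks and d their difference, the two-sided formula without continuity correction is

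n per arm = [1.96·√(2m(1−m)) + 0.842·√(p1(1−p1) + p2(1−p2))]² / d².

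Here m = 0.425 and d = 0.15, so n = [1.96·√0.48875 + 0.842·√0.4775]² / 0.0225 ≈ 169.3. This rounds up to 170 per arm, 340 in total, as stated. Power at 170 per arm is 80.2%. This calculation concerns the primary outcome and does not depend on the shock window.

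**2. Effect of counting from admission.** Let q be the share of patients who meet the shock definition before randomization, equal in both arms in expectation. Let p be the risk of shock after randomization among the rest. Then

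- scored risk = q + (1 − q)p
- risk difference = (1 − q)(p2 − p1)
- risk ratio = [q + (1 − q)p2] / [q + (1 − q)p1], which tends to 1 as q grows.

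If p1 = p2 the two scored risks are equal, so the window creates no false difference.

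**3. Illustration.** The documents give neither q nor any shock rate. The risks below are assumptions: 10% at 34°C, 20% at 31°C, 170 per arm, two-sided 5%. Power = Φ{[d√n − 1.96·√(2m(1−m))] / √(p1(1−p1) + p2(1−p2))}.

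| q | Scored risks | Difference | Risk ratio | Power |
|---|---|---|---|---|
| 0 | 10% vs 20% | 10 points | 2.00 | 74% |
| 10% | 19% vs 28% | 9 points | 1.47 | 50% |
| 20% | 28% vs 36% | 8 points | 1.29 | 35% |
| 40% | 46% vs 52% | 6 points | 1.13 | 20% |

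The q = 20% row in full: 0.20 + 0.80 × 0.10 = 0.28 and 0.20 + 0.80 × 0.20 = 0.36. Then m = 0.32, and [0.08·√170 − 1.96·√0.4352] / √0.432 = −0.38, so Φ = 35%.

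With assumed risks of 20% and 35%, power goes from 88% at q = 0 to 75% at q = 10% and 61% at q = 20%. The size depends on the rates chosen; the direction does not.

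**4. The same scenario counted from randomization.** If only post-randomization onset is counted and all 170 per arm stay in the denominator, the risks are (1 − q)p: 9% vs 18% at q = 10% and 8% vs 16% at q = 20%. The risk ratio stays at 2.00, and the same formula gives power of 68% and 62%. If the denominator is only patients free of shock at randomization (153 and 136 per arm), power is 69% and 64%. Both versions assume that patients already in shock contribute no treatment effect.

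**5. The other outcomes, read against the text.**

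- *Bleeding:* the window has the same wording. However, TIMI major or minor bleeding in Appendix 7 needs a haemoglobin fall of at least 3 g/dL (or the haematocrit equivalent) or intracranial bleeding. Section 4.4 draws a blood count on admission, and section 4.2.3 excludes several bleeding states. The effect is probably small.
- *Drug-treated arrhythmia, seizures, renal replacement:* no start time is stated, so whether earlier events count is left open.
- *Repeat arrest:* no start time either, but a repeat arrest by its name already leaves out the index arrest.

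**The case against.** **The documents do not say that pre-allocation events count.** A reader might infer that the plan scores them for all six in-hospital events: shock, bleeding, repeat arrest, arrhythmia, seizures and renal replacement. The text does not support that. For the four with no start time it is silent, and trial outcomes are ordinarily read as following allocation. The window itself brings earlier events in only for shock and bleeding, and for bleeding few should qualify.

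**Not every hypotensive patient qualifies.** This stands. Section 6.4 needs both the pressure criterion despite fluids and the support criterion, so low pressure on arrival plus an inotrope is not enough. Section 4.3 also does not say whether the balloon pump precedes the cooling catheter. The Appendix 9 guidance on refractory shock may lower q, although shock that responds to support is not covered by it.

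**The size is assumed.** This also stands. No document supplies q or an event rate, and one scenario should not be carried over to dialysis or TIMI bleeding. The trial is powered only for its primary outcome, so lost power here breaks no design commitment.

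**The dilution is not one-sided.** A reader might conclude that the window works in favour of 31°C by masking harm. It would mask a benefit just as much, and it adds no bias when the arms do not differ. Death at three time points, adverse event recording and reporting of serious events to the monitoring committee also bear on safety.

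**Restricting to patients free of shock has a price.** Patients already in shock may be those in whom deeper cooling worsens haemodynamics. Leaving them out, or assuming no effect in them, is open to challenge.

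None of this removes the main point: the stated shock window opens before allocation and nothing else in the documents closes it.

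**Conclusion.** The point holds for cardiogenic shock. Applied as written, sections 5.2 and 6.4 score shock that met the full definition before randomization, and this shrinks the risk difference by (1 − q) and moves the risk ratio toward 1. Under assumed true risks of 10% and 20%, power falls from 74% to 50% at q = 10% and 35% at q = 20%. These figures illustrate the mechanism and do not estimate what will happen in this trial.

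Bleeding shares the wording, probably with little consequence. For drug-treated arrhythmia, seizures and renal replacement the defect is a missing start time, not a wrong rule. They need the same rule so that the choice is not left to data collection or analysis. Repeat arrest does not carry the point. A reader might also infer that the main result is compromised; it is not, because the primary outcome and N = 340 do not use these windows. The change should be made, but the trial's main conclusion does not depend on it.

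**What to change.** 1. In section 5.2, define shock, bleeding, drug-treated arrhythmia, seizures and renal replacement as events with onset after randomization, counted to discharge. Bleeding keeps its stated extension of 7 days.
2. On the case report form, record the onset date and time of each event and whether the condition was present at randomization. Report presence at randomization by arm.
3. State in advance how patients with the condition at randomization are handled. Either report new onset and describe worsening separately, or analyse all randomized patients with adjustment for baseline status. The second keeps patients already in shock in the comparison.
4. Reconcile section 5.2, which sends all clinical events to blinded adjudication, with the synopsis and section 10.2, which list only death, neurologic outcome, stroke and stent thrombosis. Until that is settled, it is unclear who would date the onset of shock.

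**Cost.** Some wording in section 5.2, a few extra form fields and somewhat fewer countable events. Onset times are easiest to capture prospectively.

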The proposed study is designed to test the hypothesis that more profound cooling by achieving moderate TH will result in improved neurologic outcomes. Our aim is to answer a clinically important question in a randomized, double-blinded fashion. The trial design respects evidence from previous trials and current international guidelines. We have chosen a design that is inclusive of all patients with cardiac arrest (unless attributable to a proven intracranial bleed) for whom the treating physician wishes to incorporate therapeutic hypothermia as part of the patient's treatment plan. While previous trials have excluded patients who presented with an initial rhythm of asystole or pulseless electrical activity, we have chosen to include these patients in our study as they are routinely treated with TH in most clinical settings. Although there is no data on the use of TH in patients with an initial rhythm of asystole, we believe that these patients should be offered TH and a randomized trial to address the utility of this strategy in these patients. Lastly, our protocol design allows for discontinuation of

Commented [c1]: Reference?

cooling in patients in whom TH may be contributing to worsening clinical condition – however, data from our ROSC database and from the literature suggests this is an infrequent event^{2, 4}.

We believe that this randomized study will provide valuable clinical information for the physician and health care team treating comatose survivors of OHCA.

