Patients will be maintained at their assigned cooling temperature for a duration of 24 hours after reaching target temperature. Following the mandated 24-hour cooling period, patients will be actively re-warmed at a rate of $0.25^{\circ}\text{C}/\text{hour}$ until normothermia (36.5°C) is reached. Normothermia will be maintained for 48 hours from the time of initiation of re-warming with active management of the temperature via the ZOLL catheter. This is the current standard of practice at the University of Ottawa Heart Institute.

If, in the opinion of the blinded treating physician, cooling is contributing to intractable arrhythmia, or hypotension refractory to vasopressor use, then the treating physician may choose to abandon cooling. In this situation the temperature of the patient will be increased by 3°C (i.e. from 31°C to 34°C or from 34°C to 37°C). The treating physician will remain blinded to group allocation. If, despite the increased temperature, it is believed that cooling is still contributing to significant adverse events, the physician can request to raise the temperature again (34 to 37°C and if at 37°C then no change will be made). Blinding will be maintained.

The patient's dedicated nurse will perform all temperature changes on the ZOLL[®] machine. The nurse is the only member of the health care team that is unblinded to group allocation – for logistical reasons, blinding of the nurse is not feasible.

Aside from the difference in cooling temperatures, management in the coronary care unit and subsequently on the cardiology wards will be standard of care. Again, both the treating physicians and the patient will be blinded to treatment allocation to ensure assessment of outcomes remains unbiased.

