13.4 APPENDIX 4: SAFETY AND LABORATORY TESTS

Adverse Events and Laboratory Abnormalities

Clinical Adverse Events

An Adverse Event is any untoward medical occurrence in a patient or clinical investigation subject administered a pharmaceutical product and which does not necessarily have to have a causal relationship with this treatment. An Adverse Event can therefore be any unfavourable and unintended sign (including an abnormal laboratory finding, for example), symptom, or disease temporally associated with the use of a medicinal product, whether or not considered related to the medicinal product. Pre-existing conditions that worsen during a study are to be reported as Adverse Events.

All clinical adverse events (AEs) encountered during the clinical study will be reported on the AE page of the Case Report Form (CRF). Intensity of adverse events will be graded on a four -point scale (mild, moderate, severe, life-threatening) and reported as indicated on the CRF. Relationship of the adverse event to the treatment should also be assessed.

Laboratory Test Abnormalities

Laboratory test results will be recorded on the laboratory results pages of the CRF. Laboratory test value abnormalities as such should not be reported on the AE page of the CRF as adverse events unless they result in a clinically relevant condition.

Serious Adverse Events (SAE)

Please refer to Section 12 of the Protocol.

Treatment and Follow-up of Adverse Events

Adverse events will be followed up until they have returned to baseline status or stabilized.

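### The arrhythmia and shock outcomes depend on treatments other than the protocol's own 3°C temperature increase, which is not an outcome and is not compared by arm, so some tolerability events may be missed

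*Combined protocol and SAP*

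**What the plan says.** Three parts of the plan bear on the same clinical events.

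- **Outcomes.** Section 5.2 lists 15 secondary outcomes. Number 8 is "Arrhythmia requiring anti-arrhythmic medication (aside from beta blocker", and section 6 defines arrhythmia no further. Number 6 is "Cardiogenic shock during the initial hospitalization". Section 6.4 defines it as a systolic pressure under 80 mm Hg despite fluids and "requiring the use of intravenous inotropic support or the use of intra-aortic balloon counterpulsation". Vasopressors are not named there.
- **Response to the event.** Section 4.3 applies if the blinded physician believes that "cooling is contributing to intractable arrhythmia, or hypotension refractory to vasopressor use, then the treating physician may choose to abandon cooling". In that case "the temperature of the patient will be increased by 3°C (i.e. from 31°C to 34°C or from 34°C to 37°C". A further increase can be requested, but nothing changes for a patient already at 37°C.
- **Recording and analysis.** Appendix 4 states that "All clinical adverse events (AEs) encountered during the clinical study will be reported on the AE page of the Case Report Form (CRF", with intensity and relationship to treatment. Sections 10.3 and 12.3 send serious events to the DSMC. Section 7 plans comparisons of the primary and secondary outcomes and a description of patient comparability. It names no comparison of adverse events or of temperature increases.

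Section 4.1 says of stopping cooling in a deteriorating patient that "data from our ROSC database and from the literature suggests this is an infrequent event". It gives no figure.

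**The concern.** Both outcomes are defined by the remedy used, and the remedy written into the protocol is not one that counts. A patient whose arrhythmia settles on warming alone has no event under outcome 8. A patient whose hypotension on vasopressors leads to warming, with no inotrope or balloon pump, does not clearly have an event under 6.4. The temperature increase itself goes uncounted.

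Two things are at stake. The first is the tolerability comparison: if 31°C provokes more of these events, the trial could report a smaller absolute excess than occurred. The second is interpretation of the primary result. A first increase takes a 31°C patient to 34°C, the comparator's temperature, while analysis stays by randomized group. Without a count by arm, a reader cannot tell how much of the intended temperature contrast was delivered.

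**Working it through.** **The plan's own figures.** The plan gives no rate for arrhythmia, shock or temperature increases. Its only event-rate calculation is the sample size for the primary outcome (sections 3.6.1 and 8.1): 50% v 35%, alpha 0.05, power 80%. Taken as two-sided without continuity correction:

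n per arm = [1.960 × √(2 × 0.425 × 0.575) + 0.842 × √(0.50 × 0.50 + 0.35 × 0.65)]² / 0.15², which is just over 169 and rounds up to 170, or 340 in total (power 80.2%).

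This matches the stated 340 and does not depend on the definitions discussed here.

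**The definitions side by side.**

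| Event and management | Counts under 5.2 / 6.4? |
|---|---|
| Arrhythmia, anti-arrhythmic drug (not a beta blocker), then warming | Yes, outcome 8 |
| Arrhythmia, warming with no such drug | No |
| Pressure < 80 mm Hg despite fluids, inotrope or balloon pump, then warming | Yes, outcome 6 |
| Hypotension on vasopressor only, then warming | Not clearly; vasopressors are not named in 6.4 |
| Repeat arrest with CPR | Yes, outcome 7, whatever else is done |
| The temperature increase itself | No |

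The possible loss is confined to the second and fourth rows.

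**Effect of missed events on a comparison.** Let p be the true event rate in an arm and f the fraction of events with no qualifying treatment.

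- Counted rate = p × (1 − f).
- Counted ratio = true ratio × (1 − f at 31°C) / (1 − f at 34°C).
- The counted difference is smaller than the true one when p × f is larger at 31°C than at 34°C.

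Illustration with assumed true rates of 30% (31°C) and 20% (34°C):

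| Missed at 31°C | Missed at 34°C | Counted rates | Difference (points) | Ratio |
|---|---|---|---|---|
| 0% | 0% | 30.0% v 20.0% | 10.0 | 1.50 |
| 10% | 10% | 27.0% v 18.0% | 9.0 | 1.50 |
| 10% | 5% | 27.0% v 19.0% | 8.0 | 1.42 |
| 20% | 10% | 24.0% v 18.0% | 6.0 | 1.33 |
| 10% | 20% | 27.0% v 16.0% | 11.0 | 1.69 |

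Equal missing shrinks the absolute difference and leaves the ratio alone. The ratio falls only if proportionally more events are missed at 31°C, and it rises if more are missed at 34°C. For scale, 10% missed at a true rate of 30% is 3% of 170, about 5 patients.

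**The number of steps differs by arm.** From 31°C two increases take effect (31 to 34 to 37). From 34°C only one does (34 to 37). A count of increases is therefore not comparable between arms. The proportion of patients with at least one increase is.

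**The case against.** Much of the case on the other side stands.

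- **Warming comes late.** Section 4.3 reserves it for arrhythmia that is intractable or hypotension that has already failed vasopressors. Many such patients will have had an anti-arrhythmic drug, an inotrope or a balloon pump, and will count. This stands, so it would be wrong to say that events managed by warming are, as a class, uncounted. But an intractable arrhythmia need not have been treated with a drug, and a vasopressor is not a listed qualifier in 6.4.
- **The events are recorded anyway.** Adverse event pages, serious event reports and the separate outcomes of repeat arrest and death capture harm. This stands for recording but not for comparison, since section 7 names no analysis of adverse events by arm. Section 7.3 does promise a description of in-hospital interventions and course. That could be stretched to cover temperature increases, but it does not name them.
- **No direction is shown.** A reader might infer that harm at 31°C will be understated. With assumed true rates of 12% v 6%, and half the events missed at 31°C against a quarter at 34°C, the counted rates are 6.0% v 4.5% and a 6-point excess appears as 1.5. The ratio falls from 2.0 to 1.33 only because the missed fraction was set twice as high at 31°C. With half missed in both arms the rates are 6.0% v 3.0%, still a ratio of 2.0. The example also needs 12% × 0.5 = 6% of 170, about 10 patients at 31°C, to be missed, which fits poorly with an event expected to be infrequent. The option exists in both arms and is requested by a blinded physician, and nothing in the documents fixes the missed fractions.
- **A broader outcome is still remedy-based.** It would rest partly on the physician's opinion that cooling contributed. This stands, and is why the present definitions should be kept on their own line.

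**Conclusion.** The gap is real but limited. The protocol's own response to two named harms satisfies neither matching outcome definition, is not itself an outcome, and has no named comparison by arm, so some events may be missed by the secondary outcomes. If 31°C truly causes more events, the absolute excess would be understated unless the missed fraction at 34°C exceeds that at 31°C by at least the true rate ratio. Both the premise and the missed fractions are unknown, so neither the direction nor the size of any bias is established. All rates used here are assumptions. The primary outcome, death or DRS above 5, and the sample size are untouched. This is a cheap improvement to safety reporting that also makes the delivered temperature contrast visible. It does not show that the trial hides harm.

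**What to change.** 1. Add to section 5.2 a secondary safety outcome: any temperature increase under 4.3, with reason and time. Compare the proportion of patients with at least one increase by randomized arm, and only describe second increases.
2. Let an arrhythmia that led to a temperature increase qualify under outcome 8. Report hypotension that led to one alongside outcome 6. Keep both present definitions as a separate line, and state whether vasopressor use counts under 6.4.
3. Record the event, reason and time on one CRF line. Section 4.2.5 describes the nurse's log only as charting temperature, so the reason has to be newly collected.
4. Give adjudicators the fact of a request, not the temperatures, because an entry of 31 to 34 or 34 to 37 reveals the allocation.

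The cost is outcome wording, one CRF line and a masking instruction. The downside is broader outcomes that depend partly on physician judgement. The clinical rule in 4.3 does not change.
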